9.9. Sample Handling

9.9.1 Sample handling for study purposes

Salivary samples (2mls in a universal container pot) will be obtained for measuring of salivary cortisol levels, for study purposes only. Samples will be obtained upon awakening after each night (e.g. at 6am).

9.10. Early Discontinuation/Withdrawal of Participants

During the course of the study a participant may choose to withdraw or be withdrawn early from the study at any time. This may happen for several reasons, including but not limited to:

- The occurrence of what the participant perceives as an intolerable AE.
- Inability to comply with study procedures
- Participant decision

Participants may also withdraw their consent, meaning that they wish to withdraw from the study completely. According to the design of the study, participants can withdraw but permit data and samples obtained up until the point of withdrawal to be retained for use in the study analysis. No further data or samples would be collected after withdrawal.

In addition, the Investigator may discontinue a participant from the study at any time if the Investigator considers it necessary for any reason including, but not limited to:

- Ineligibility (arising during the study)
- Significant protocol deviation
- Significant non-compliance with treatment regimen or study requirements
- Clinical judgement

We do not expect significant adverse events from the stimulation patterns applied. However, there may be an impact on performance upon awakening in the case where sleep stage/depth perturbations are achieved. When DBS devices are turned off/switched to lower than clinical settings, there may be a transient return to pre-treatment baseline or deterioration in symptoms. With regards to chronic pain patients, this might be uncomfortable. However, this eventuality will be mentioned during recruitment and clearly stated in the patient information sheet. In addition, there will be clinical supervision during the perturbations. If the participant is concerned and/or experiences discomfort because of either this or a deterioration in sleep depth and quality, they will be reminded that they can withdraw at any time without any impact of further care.

Decision for withdrawal of participants who experience an effect but wish to continue will lie with the site PI and the clinical team. If the participant is withdrawn due to an adverse event, the Investigator will arrange for a follow-up clinic visits or telephone calls until the adverse event has resolved or stabilized. The type of withdrawal and reason for withdrawal will be recorded in the

CRF. Should the minimum required number of participants per cohort not be met, or if there is a relative imbalance per patient number per cohort, withdrawn participants will be replaced.

9.11. Definition of End of Study

The end of study will be the date of the last visit of the last participant.

10. SAFETY REPORTING

10.1. Definition of Serious Adverse Events

A serious adverse event is any untoward medical occurrence that:

- results in death
- is life-threatening
- requires inpatient hospitalization or prolongation of existing hospitalization
- results in persistent or significant disability/incapacity

Other 'important medical events' may also be considered a serious adverse event when, based upon appropriate medical judgement, the event may jeopardize the participant and may require medical or surgical intervention to prevent one of the outcomes listed above.

NOTE: The term "life-threatening" in the definition of "serious" refers to an event in which the participant was at risk of death at the time of the event; it does not refer to an event which hypothetically might have caused death if it were more severe.

10.2. Reporting Procedures for Serious Adverse Events

A serious adverse event (SAE) occurring to a participant should be reported to the REC that gave a favorable opinion of the study where in the opinion of the Investigator the event was 'related' (resulted from administration of any of the research procedures) and 'unexpected' in relation to those procedures. Reports of related and unexpected SAEs should be submitted within 15 working days of the Investigator becoming aware of the event.

It is a requirement of the funder that unanticipated problems involving risk to subjects or others must be promptly reported. This will be done by telephone (██████████), by email (██████████), or by facsimile (██████████) to the HRPO. A complete written report will follow the initial notification. In addition to the methods above, the complete report will be sent to the Funder, at a designated address (US Army Medical Research and Development Command, ██████████).

Suspensions, clinical holds (voluntary or involuntary), or terminations of this research by the Institutional Review Board (IRB), the institution, the Sponsor, or regulatory agencies will also be promptly reported to the USAMRDC ORP HRPO.

The results of the analysis of previously data from the investigational RC+S device will be submitted to the FDA.

11. STATISTICS AND ANALYSIS

11.1. Statistical Analysis Plan (SAP)

The plan for the statistical analysis of the study are outlined below. There is not a separate SAP document in use for the study.

11.2. Description of the Statistical Methods

All analyses will be performed using commercially available software including MATLAB and SPSS. We will use a combination of novel techniques as well as existing and previously published approaches to signal analysis of EEG data, classification and testing for statistical significance. Parametric and non-parametric statistical testing procedures may be employed.

A Hidden Markov Model (HMM) can be generated for each patient, to assist in a statistical comparison of the effect of electrical perturbation of the brain. HMM states will be based on observations made by currently utilized metrics, such as EEG activity in different frequency bands, while the algorithm used for HMM will be based on literature (Vidaurre et al. 2018). A Hidden Markov Model (HMM) will be updated for each disease state, and patient, to add additional data for the stimulation matrix.

We will further assess correlations between stimulation perturbations and observed cognitive measures, physiological biomarkers (cortisol), subjective questionnaires, and post-hoc analysis of sleep patterns. Comparisons between patients control nights will provide a general assessment of in-patient variability. With the limited dataset, areas of statistical significance will be assessed. Where statistical analysis is not possible, consistency and data trends will be evaluated.

Outcomes (primary, secondary, tertiary) have been described in section 6 page 14, while comparators and interventions described in section 9.6 page 20.

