9.6.2. Description of comparator(s)

We will use both within- and between-subject comparators. As within-subject comparators, these will primarily be the usual patient settings of low frequency (LF) or high frequency (HF) continuous stimulation (ON) at the clinically prescribed amplitude and frequency. Therefore, we will be able to make assumptions both about these settings (beneficial/disruptive) and the intervention, with regards to effects on EEG patterns, autonomic activity, behavioural measures etc. In addition, since we will be applying a number of exploratory patterns per night (according to sleep stage), each of these will be used as a comparator to others. Where electrical stimulation will be switched off (OFF), this will be compared to individual stimulation configurations as well as all (ON) states. Where comparable stimulation patterns will be used in different patient groups (e.g. HF stimulation during NREMS2 in both HC and ANT), these will serve as between-subject comparators. In addition, given the exploratory nature of this study, the responses of different participants to the same stimulation pattern will be compared (e.g. effects on sleep stages/EEG rhythms of stimulation during REM, between patients with hippocampal electrodes).

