9.7. Visit-2 First EMU study visit

Baseline characterization of sleep and perturbations

Baseline day:

Upon the first day of their arrival to Saint Marys Hospital, patients will be familiarized with the testing battery and EEG equipment. We will run the battery of questionnaires and tests while participants are on their usual stimulation parameters and medications, to ensure that delays/errors when this is repeated upon awakening are not a result of task novelty.

Based on each patient’s sleep diary and actigraphy from their Empatica watch, we will determine a bedtime that corresponds with their usual schedule. The gold standard polysomnography will be used to measure scalp EEG and sleep over two nights in each participant. One night will be used to characterize a patient’s sleep state with their typical therapy parameter settings (stimulation on) or off stimulation, while during the other night effects of defined perturbations (examples outlined in Figures 1-5 in the Appendix) on sleep we be assessed. Medications and other influences will be controlled as much as possible between the control and the experiment (i.e. consistent with their daily medication dose). Patients will be under supervision of trained clinical personnel.

For these two nights, we will configure each subject with the polysomnography system and programmer. This will provide a consistent environment over both nights.

Baseline night: The main purpose of this first night of recording is for the researcher to become familiar with the patient's typical sleep patterning /sleep stages and their electrophysiological and polysomnographic correlates. For this we will capture and quantify the EEG in different stages (WAKE, N1, N2, N3, REM) and observe respiratory and autonomic parameters. Should we be able to recruit patients with DBS devices that enable us to sample intracranial data, we will also record samples of data during different sleep stages.

At the end of the night, we will define the dominant EEG characteristics for each sleep stage and translate this to transition models for each patient. The outcome of this analysis will be used to generate the patient-specific stimulation perturbations based on sleep stages. Data collected during the first (baseline) night will be used as the baseline for the remainder of the protocol.

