9.8. Visit-3 Second EMU visit

The second visit will also consist of two nights of sleep recordings. We will once again connect the participant to the equipment and capture standard behavior and electrophysiological nature of brain in different stages (AWAKE, N1, N2, N3, REM) as well as intracranial data where available. This will happen at the beginning of both nights and be compared to the baseline. This visit will be largely informed by the sleep characteristics and stimulation results of the first visit.

Adaptive night: We will use real-time classification of sleep architecture to perturb the networks with variants of stimulation. The perturbations will be automatically generated by the adaptive algorithm, which will be informed from the data gathered during the first visit.

Control night: open loop stimulation (or off) will be applied, guided again by data obtained during the first visit.

Upon waking, salivary cortisol samples will be obtained as before. The cognitive tasks will be performed again to assess sleep inertia and other response variables. Subjective questionnaires will be administered post-cognitive screen. Cognitive tests will continue for an additional post-wake to fully gauge impacts on sleep inertia. Testing and questionnaire schedule will be the same during both visits.

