11.5. Decision points

As specified in section 9.7., interim analyses of each patient's baseline data will be performed after the first night of the first visit. This will help establish a familiarity with each participant's sleep stage duration and EEG morphology, their maximum sleep depth as well as the presence of pathological sleep features. Based on this knowledge, decisions on the timing of the stimulation during the second night will be made by the PI and sleep scientist team, as well as basic assumptions on the desired effects. Following the first visit, further interim analyses will determine to what degree these assumptions were correct, so that stimulation patterns can be explored further during the second visit.

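### Section 11.2 does not say how its correlations of stimulation with cognition, cortisol and questionnaires handle repeated nights or patient differences; if patient-nights are pooled, tailoring can produce correlations when stimulation does nothing

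*Combined protocol and SAP*

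**What the plan says.** Section 11.2 describes the analysis linking stimulation to the waking and daytime outcomes in one sentence: "We will further assess correlations between stimulation perturbations and observed cognitive measures, physiological biomarkers (cortisol), subjective questionnaires, and post-hoc analysis of sleep patterns". On tests it adds only that "Parametric and non-parametric statistical testing procedures may be employed". It does not say whether the unit is the night or the patient, how a perturbation becomes a number, or whether a patient effect or baseline value enters. Section 11.1 confirms that no separate SAP exists. Section 6 lists test-battery performance as a secondary outcome and cortisol as a tertiary one.

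Stimulation is set patient by patient. After the baseline night, Section 9.7 says: "The outcome of this analysis will be used to generate the patient-specific stimulation perturbations based on sleep stages". Section 11.5 adds that "decisions on the timing of the stimulation during the second night will be made by the PI and sleep scientist team". For the second hospital stay, Section 9.8 says: "This visit will be largely informed by the sleep characteristics and stimulation results of the first visit".

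Section 11.3 gives 15 patients as the lower bound and three stimulation nights per patient. On reference conditions, Section 9.6.2 names the patient's usual settings as the main within-subject comparator, and Section 9.7 says: "Data collected during the first (baseline) night will be used as the baseline for the remainder of the protocol". Section 9.6.2 also plans comparison across patients: "the responses of different participants to the same stimulation pattern will be compared".

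**The concern.** Saliva is collected once after each night. The waking tests are repeated within a morning, but all repeats follow the same night of stimulation. For these outcomes a patient therefore supplies about three stimulation values, too few for a useful correlation in one person, so patients have to be combined in some way.

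The simplest way is one correlation over all patient-nights. That has two faults here. First, a stable characteristic of the patient (disease, target, usual sleep) may influence both the pattern chosen and the usual level of vigilance, mood or cortisol. The correlation then carries this patient-level link as well as any effect of stimulation. Second, nights from one patient are alike, so the test behaves as if it had more information than it has.

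At stake is whether a reported link with sleep inertia or cortisol is read as an effect of stimulation when it only shows how patterns were allocated.

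**Working it through.** **Inputs from the plan (Section 11.3).** Five electrode locations × 3 patients = 15, which reproduces the stated lower bound. Three stimulation nights each give 15 × 3 = 45 patient-nights. The plan gives no effect size, standard deviation, intraclass correlation (ICC) or numerical significance level.

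**Assumptions.** Two-sided 0.05; outcome ICC 0.4-0.8; share *w* of the stimulation variance lying between patients 0, 0.2 or 0.5; relation ρ between the patient part of stimulation and the patient's usual outcome level 0, 0.3 or 0.5.

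**Model with no stimulation effect** (patient *i*, night *j*):
- outcome: y = √ICC·u_i + √(1−ICC)·e_ij
- stimulation: x = √w·v_i + √(1−w)·e′_ij, with corr(u, v) = ρ

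The pooled test has 45 − 2 = 43 df. The within-patient test (both variables centred on the patient's mean) has 15 × 2 − 1 = 29 df.

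**Check by formula.**
- Expected pooled correlation = ρ·√(w·ICC). With ρ = 0.5, w = 0.5, ICC = 0.5 this is 0.5 × √0.25 = 0.25. The simulated mean is 0.235.
- With ρ = 0 the expected correlation is zero, but its variance is inflated by about 1 + (3 − 1)·w·ICC. With w = 0.5, ICC = 0.5 this is 1.5, so the 1.96 limit acts like 1.96/√1.5 = 1.60, a two-sided error of about 11%. The simulation gives 10.6%.
- With w = 0 both problems vanish and the error is 5%.

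**Simulated false-positive rates, 15 patients × 3 nights** (ranges are over ICC 0.4-0.8):

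| Share of stimulation variance between patients | ρ = 0 | ρ = 0.3 | ρ = 0.5 |
|---|---|---|---|
| Pooled, 50% | 10-15% | 18-31% | 33-54% |
| Pooled, 20% | 7-9% | 10-15% | 16-27% |
| Pooled, 0% | 5% | 5% | 5% |
| Within-patient, any share | about 5% | about 5% | about 5% |

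More patients do not help. At ICC 0.6, ρ = 0.3 and a 50% share, the pooled rate is 24% with 15 patients, 37% with 30 and 51% with 50. The Synopsis expects 30-50 participants over the duration of the study.

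**Power** (true within-patient slope 0.35, ICC 0.6). With 20% of the variance between patients: 62% pooled, 73% within-patient. With 50%: 60% pooled, 54% within-patient. Pooled power is partly bought with its raised error rate.

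**Feedback between visits.** Suppose patterns depend on the preceding visit's outcome, ICC is 0.5 and there is no stimulation effect. At dependence 0.3, 0.5 and 0.7, patient-mean centring alone gives 6.6%, 11.2% and 19.2% false positives, with mean correlation −0.07, −0.13 and −0.20. A chance high value at visit 1 raises the later stimulation values while the later outcomes fall back, and centring turns this into a negative slope. A contrast between the two second-visit nights avoids it if both nights draw equally on the first visit, because the shared part cancels.

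**The case against.** The strongest reply is that the plan nowhere says patients will be pooled. It names within-subject comparators, sets the patient's own first night as baseline, allows a Hidden Markov Model per patient and cites an N-of-1 design. A reader might infer from Section 11.2 that patient differences will be ignored; the documents do not support that. They are silent on it. What remains is that none of these elements is tied to the correlations, and the Hidden Markov Model states are built from metrics such as EEG band activity, not from vigilance or cortisol.

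Three further limits stand.
- The quoted sentence also covers sleep patterns. Section 11.3 expects many stimulation epochs per patient, so those correlations can be computed within one patient. The point applies to outcomes tied to a night.
- The documents do not say that patients who sleep or perform worse receive a different pattern. Night-2 tailoring rests on features such as EEG form, stage duration, sleep depth and pathological sleep features, and the Appendix A examples vary stimulation by sleep stage. A non-zero ρ is plausible but assumed.
- The outcomes are secondary or tertiary in a feasibility study, and Section 11.2 allows for looking at trends. It also says that statistical significance will be assessed, so the error rate still matters.

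**Conclusion.** The concern holds in a limited form. The correlations are unspecified, and the most direct way of computing them for night-level outcomes can give a correlation with no stimulation effect. The false-positive rate is about 10-54%, 7-27% or 5% when half, a fifth or none of the stimulation variance lies between patients, with ρ from 0 to 0.5 and ICC 0.4-0.8. The documents give none of these values. At ρ = 0 the excess comes only from counting repeated nights as independent.

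Two stronger conclusions are tempting and not supported. One is that spurious correlations will appear: that needs pooling, stimulation that differs between patients and, for a biased coefficient, a stable trait linked to both stimulation and outcome. The other is that a within-patient analysis is unbiased and more powerful in general: its 5% rate assumes no feedback between visits, which Section 9.8 makes doubtful, and its power advantage reverses when half of the stimulation variance is between patients.

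The change should be made. It does not affect recruitment or the assessment of feasibility.

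**What to change.** In Section 11.2, for cognitive measures, cortisol and questionnaires:

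1. Replace the correlations by a within-patient association: a mixed model with a patient intercept and stimulation centred on each patient's own mean, or a repeated-measures correlation. Include night order as a covariate, and define the stimulation variable.
2. Report the between-patient association separately, labelled as reflecting how patterns were chosen.
3. Because second-visit patterns depend on first-visit results, also adjust for the preceding visit's outcome or show the visits separately. Describe the within-patient slope as exploratory.

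The cost is SAP wording; the methods are available in the MATLAB and SPSS software already named. Patients with one usable stimulation night add nothing to the slope. Shown separately, the first visit has only one stimulation night, so it can contribute only a contrast with the baseline night. Power can be slightly lower than with pooling when much of the stimulation variance is between patients.

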11.3. Sample Size Determination

This is a feasibility study into recruiting and conducting the study procedures in patient populations. Given the exploratory and novel nature of this study, effect sizes are as of now, unknown. We are collecting from different groups bearing in mind that a minimum n=3 is required for the most rudimentary statistics based on patient number. We therefore expect 15 patients to be the lowest bound for 5 different DBS electrode locations. There will be multiple comparable stimulation epochs per patient, across three nights (second night of first visit and both nights of second visit). The number of sleep stages and cycles per night will vary between participants, with an added unknown being the effect of the disease state on sleep. However, this within- and across-subject comparison will boost statistical power. Further support that an N-of-1 trial design can be used for closed-loop DBS research and provide individualized, precision data to inform device development, was published recently (Stevens and Gilbert 2020).

11.4. Analysis populations

All data collected from participants who have completed the full study will be included in the analysis.

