6. OBJECTIVES AND OUTCOME MEASURES

Objectives	Outcome Measures	Timepoint(s) of outcome measure
Primary Objectives		
Feasibility of study	Ability to recruit planned participant number and carry out scheduled experiments in reproducible fashion	
 Analyses post-study completion Some evidence during interim analyses per group
Effect of stimulation on sleep stages	EEG changes (frequency changes, changes in EEG patterns and sleep structure)	
 During stimulation Post-stimulation at specific sleep stages

Secondary Objectives
 
Effect of stimulation on sleep inertia and vigilance & performance during the day
 
Controlling sleep depth and sleep-wake transitions
	
Performance on short and long test battery (see section 9.6.3)
 
Assessment of effect on latency to sleep onset and REM sleep, number of sleep cycles, duration of sleep stages, number of awakenings per night, sleep efficiency
	
 Upon awakening (post-baseline night and post-intervention) During the day (post-baseline and intervention) During intervention nights

Tertiary Objectives
 
Effect of stimulation on other measures of arousal
	
Effect on autonomic measures such as heart-rate variability and blood pressure, as well as salivary cortisol levels
	
 Overnight measurements Salivary cortisol levels measured upon awakening each day (6am).

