9.4. Enrollment

Patients enrolling in the study will be recorded in an encrypted study database on a password-protected Mayo Clinic computer. The team will identify patients who have been previously implanted with a DBS device and a contact call will be scheduled after liaison between the clinical team. During this, visit times and traveling arrangements will be discussed.

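### Section 11.4 names only participants who completed the full study as the analysis population; this does not fit the withdrawal rule in 9.10, and the feasibility outcome has no stated denominator

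*Combined protocol and SAP*

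**What the plan says.** Section 11.4 is a single sentence: "All data collected from participants who have completed the full study will be included in the analysis". No other analysis population is defined, and section 11.1 closes off another source: "There is not a separate SAP document in use for the study".

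Section 9.10 treats people who leave early differently. It says that "participants can withdraw but permit data and samples obtained up until the point of withdrawal to be retained for use in the study analysis". It also says "The type of withdrawal and reason for withdrawal will be recorded in the" CRF, and provides for replacement where a cohort misses its minimum "or if there is a relative imbalance per patient number per cohort, withdrawn participants will be replaced".

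Section 6 lists feasibility first among the primary objectives, with the outcome "Ability to recruit planned participant number and carry out scheduled experiments in reproducible fashion". On the recruitment side, section 9.4 says "Patients enrolling in the study will be recorded in an encrypted study database".

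For the stimulation effect, section 9.7 makes the first night the baseline for everything that follows, and section 11.3 counts three later nights as stimulation nights. Section 9.6.2 adds comparisons between patterns applied within a night, and: "Where electrical stimulation will be switched off (OFF), this will be compared to individual stimulation configurations as well as all (ON) states". Section 11.8 allows all or part of a participant's data to be dropped for poor recording quality. Section 11.6 ends the study once the target number has been 'recorded', without defining that word.

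**The concern.** Under a heading about analysis populations, a sentence restricted to completers will normally be taken to exclude everyone else. An analyst who follows it would set aside data that 9.10 keeps for analysis. An analyst who starts from 9.10 would include them. With no separate SAP, nothing settles which set is right.

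Two things are at stake. First, people who leave early can still provide usable within-person comparisons, and section 11.3 relies on such comparisons in cohorts that may have only 3 participants. Excluding leavers also selects on tolerating the study. Second, whether the four-night schedule can be carried out is part of a primary outcome. A set defined by completion cannot show failure to complete, and replacing those who withdraw can hide it further. The plan collects the information needed but does not say what it will be counted against.

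**Working it through.** **The plan's own figure.** Section 11.3 takes a minimum of 3 patients in each of 5 electrode locations: 5 × 3 = 15. This reproduces, and contains no allowance for dropout.

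**The two sections side by side.**
- *11.4 read as a definition of the set:* completers are in and others are out. Permitted pre-withdrawal data then have no place in the analysis, which does not fit 9.10.
- *11.4 read strictly literally:* completers are in and others are not mentioned. Nothing contradicts 9.10, but 11.4 gives leavers no place in any analysis set.

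Either way the sentence needs rewording.

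**Data lost in one small cohort.** Take 3 completers and one participant who leaves after the first visit. The schedule is one baseline night (9.7) and three stimulation nights (11.3). A pair is a participant with the baseline night and at least one stimulation night.
- Pairs available: 3 + 1 = 4. A completers-only set keeps 3, so 1 of 4 is lost.
- Stimulation nights recorded: 3 × 3 + 1 = 10. A completers-only set keeps 9, so 1 of 10 is lost.
- The leaver's within-night and OFF-versus-ON comparisons (9.6.2) are lost as well.

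**Completion rate, with assumed dropout.** The documents give no dropout rate. Assuming 10%, 20% or 30%, the enrolment needed to expect 15 completers is 15/0.9 = 16.7, 15/0.8 = 18.75 and 15/0.7 = 21.4, rounded up to 17, 19 and 22. Completion with an exact (Clopper-Pearson) 95% interval:

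| Enrolled | Completers | Completion | 95% CI | In a completers-only set |
|---|---|---|---|---|
| 17 | 15 | 88% | 64% to 99% | 15/15 = 100% |
| 19 | 15 | 79% | 54% to 94% | 15/15 = 100% |
| 22 | 15 | 68% | 45% to 86% | 15/15 = 100% |

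**Data lost over the whole study, same assumption.** With 15 completers and d = 2, 4 or 7 leavers, all leaving after night k, the stimulation nights discarded are (k − 1)d out of 45 + (k − 1)d.
- After night 1: none, and no pair existed to lose.
- After night 2 (end of first visit): 2/47 = 4%, 4/49 = 8%, 7/52 = 13%.
- After night 3: 4/49 = 8%, 8/53 = 15%, 14/59 = 24%.

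In the last two cases 2, 4 or 7 pairs are also lost.

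**Replacement.** If one of 3 participants in a cohort withdraws and is replaced by someone who completes, 4 were enrolled and 3 completed (3/4 = 75%). The completers-only set shows 3/3.

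**The case against.** The strongest reply is that 11.4 contains no word such as 'only'. It can be read together with 9.10: completers' data are all used, and leavers' data are used up to withdrawal if they permit. 9.10 is the specific provision and states analysis as its purpose. This stands as far as it goes. A reader might infer that the two sections flatly contradict each other, and the text does not support that. It supports a poor fit on the natural reading and a gap on the literal one.

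A reader might also infer that feasibility will be reported as 100% completion. The plan never says that feasibility is computed within the 11.4 set. Enrolment and withdrawals are logged (9.4, 9.10), and section 6 allows some feasibility evidence from interim analyses. What remains is that no denominator is stated, so the 100% figure applies only if the 11.4 set is used.

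Nor does section 11.5 help to show an inconsistency. Its interim analyses are per-patient reviews that guide that patient's next stimulation, and they say nothing about membership of the final set.

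Replacement does protect cohort minimums. It does not recover data already recorded, and it does not say how the person replaced is counted.

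Finally, this is an unblinded exploratory study with no power calculation, and every dropout figure above is assumed. That is right. The figures show scale, and the point does not depend on them.

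**Conclusion.** The concern holds in this limited form. The plan's only population statement names completers alone, sits badly with 9.10 and leaves leavers undefined at best. No denominator is given for the feasibility outcome. This should be fixed before analysis, but it does not undermine the design, because the information needed is already being collected.

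The one figure that needs no dropout rate is conditional: with 3 completers and one participant leaving after the first visit, a completers-only set loses 1 of 4 baseline-stimulation pairs. The completion rates of 88%, 79% and 68%, and the 0% to 24% of stimulation nights lost, rest on assumed dropout and on all leavers going at the same point. A reader might infer that the stimulation results would be biased in a favourable direction. Selection on tolerating the study is possible, but nothing in the documents gives its direction or size.

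**What to change.** Replace 11.4 with two sets.

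1. **Feasibility set:** all consented participants confirmed eligible. Because section 9.2 takes consent before screening, report screen failures separately. Report the number recruited against plan, nights completed out of 4, and withdrawals with reasons. Keep replaced participants in the denominator, and report recordings excluded under 11.8, in whole or in part, against it.
2. **Effect set:** all participants with usable data for at least one planned comparison, using data up to withdrawal where permitted, as in 9.10. Require the baseline night only for comparisons against baseline, so that the within-night and OFF-versus-ON comparisons in 9.6.2 do not depend on it. Keep completers-only as a sensitivity analysis.

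Cross-refer 11.4 and 9.10, say in 9.10 how replaced participants count, and say in 11.6 whether 'recorded' means enrolled or completed.

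The cost is new wording in 11.4, a sentence each in 9.10, 11.6 and 11.8, and a little more analysis. No extra patients, visits or data are needed. The reported feasibility figure may be less favourable.
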